2.2 RISK/BENEFIT ASSESSMENT

2.2.1 KNOWN POTENTIAL RISKS

There are several potential risks or discomforts involved with being in this study. These are outlined below. There may be uncommon or previously unknown risks.

Mepolizumab risks:

Hypersensitivity reactions (e.g., anaphylaxis, angioedema, bronchospasm, hypotension, urticaria, rash) have occurred following administration of mepolizumab. These reactions generally occur within hours of administration but in some instances can have a delayed onset (i.e., days). In the event of a hypersensitivity reaction, mepolizumab will be discontinued.

The most common adverse reactions ($\geq 3\%$ and more common than placebo) reported in the first 24 weeks of 2 clinical trials for severe asthma with mepolizumab (and placebo) were: headache, 19% (18%); injection site reaction, 8% (3%); back pain, 5% (4%); fatigue, 5% (4%); influenza, 3% (2%); urinary tract infection, 3% (2%); abdominal pain upper, 3% (2%); pruritus, 3% (2%); eczema, 3% (<1%); and muscle spasm, 3% (<1%).

Systemic Reactions, including Hypersensitivity Reactions: In 3 clinical trials, 3% of subjects who received 100 mg of mepolizumab experienced systemic (allergic and nonallergic) reactions, compared to 5% in the placebo group. Up to 6% (2% in HES, 6% in EGPA) of subjects who received 300mg of mepolizumab experienced systemic (allergic and nonallergic) reactions, compared to up to 1% (0% HES; 1% EGPA) in the placebo group.

Systemic allergic/hypersensitivity reactions were reported by 1% of subjects who received 100mg of mepolizumab, compared to 2% of subjects in the placebo group. Manifestations included rash, pruritus, headache, and myalgia. In EGPA and HES trials using 300mg of mepolizumab, rates of systemic allergic/hypersensitivity reactions were 4% (1% placebo) and 0% (0%), respectively. Manifestations included rash, pruritus, flushing, fatigue, hypertension, warm sensation in trunk and neck, cold extremities, dyspnea, and stridor.

Systemic nonallergic reactions were reported by 2% of subjects who received 100mg of mepolizumab and 3% of subjects in the placebo group. Manifestations included rash, flushing, and myalgia. A majority of the systemic reactions were experienced on the day of dosing. In EGPA and HES trials using 300mg of

mepolizumab, rates of systemic nonallergic reactions were 1% (0% placebo) and 2% (0%), respectively. Manifestations observed included angioedema (EGPA) and multifocal skin reaction (HES).

Injection site reactions (e.g., pain, erythema, swelling, itching, burning sensation) have been reported at a rate of 8% in subjects treated with 100mg of mepolizumab, compared with 3% in subjects treated with placebo. In trials using a 300mg dose of mepolizumab, injection site reactions have been reported at a rate of 15% (13%) in clinical trials for Eosinophilic Granulomatosis with Polyangiitis and at 7% (4%) in clinical trials for Hypereosinophilic Syndrome.

In controlled clinical trials, 2 serious adverse reactions of herpes zoster occurred in subjects treated with mepolizumab compared to none in placebo.

Eosinophils may be involved in the immunological response to some helminth infections. Patients with pre-existing helminth infections were excluded from participation in the clinical program. Patients with pre-existing helminth infections should be treated for their infection prior to mepolizumab therapy. If patients become infected whilst receiving treatment with mepolizumab, and do not respond to anti-helminth treatment, temporary discontinuation of mepolizumab should be considered.

While clinical experience does not support a role for mepolizumab in the development of malignancies, long-term animal studies have not been performed. Published literature using animal models suggests that IL-5 and eosinophils are part of an early inflammatory reaction at the site of tumorigenesis and can promote tumor rejection. However, other reports indicate that eosinophil infiltration into tumors can promote tumor growth. Therefore, the malignancy risk in humans from an antibody to IL-5 such as mepolizumab is unknown.

When reducing concomitant steroids and/or immunosuppressant treatment, the potential to unmask malignancies should be considered in the management of any subject receiving mepolizumab. Subjects with lymphoproliferative HES or those with an abnormal T-cell phenotype are at increased risk of developing T-cell lymphoma as part of the natural history of the disease. T-cell lymphoma has been reported in HES patients receiving mepolizumab. It is not known if the risk of T-cell lymphoma in susceptible patients is increased by treatment with immunomodulators such as mepolizumab. The risk benefit in these patients should be considered prior to initiation and/or continuation of treatment with mepolizumab.

Mepolizumab is considered to have a low potential for drug-drug interactions because it selectively binds and neutralizes the cytokine IL-5. There are no reports of IL-5 receptors being expressed on hepatocytes. Neutralization of IL-5 is, therefore, not expected to alter gene expression of cytochrome P450 or transporters. Therefore, no formal drug interaction studies have been conducted.

For additional information, please refer to the latest version of the package insert (study Investigator Brochure).

EGD with biopsy risks:

The endoscopy is a well-established procedure with a very low rate of complications. Endoscopy and biopsy are the best methods for monitoring EoE disease activity. People with EoE may normally need repeated endoscopies every year. Briefly, risks include mild discomfort due to gagging while the tube is passed down the throat. Subjects may also experience mild sore throat, chest pain or discomfort,

abdominal pain or discomfort, or painful or difficult swallowing following the procedure. Medicines may ease these problems. Rare risks from an endoscopy include bleeding and infection. There is a very small risk (about 3 in 10,000) of esophageal perforation that could require surgery to repair and a similarly small risk (8 in 10,000) of aspiration that could cause pneumonia.

The number of biopsies taken for this study is within the spectrum of routine clinical practice for esophageal diseases and EoE in particular. Nevertheless, there is a very small risk of perforation or significant bleeding that would require a blood transfusion or other measures to stop the bleeding. To minimize this risk, subjects will be monitored for any bleeding during the biopsy portion of the procedure, and if bleeding is heavy, clinically indicated actions to stop the bleeding will be performed, and further biopsy procurement will be stopped.

There is a risk of adverse reaction to the anesthetic or medication used for the endoscopy. These reactions may require treatment. There may be inflammation of the vein through which medication is given. Subjects with asthma have an increased risk for problems with the anesthesia. An adverse reaction to the medications used for the endoscopy can include difficulty breathing, respiratory depression, low blood pressure, slow heart, excessive sweating, spasms in the larynx, an allergic reaction, such as hives and itching or anaphylaxis.

After the endoscopy, subjects may experience pain in the throat or neck, vomiting, black or bloody stools, pain in the chest or abdomen, or fever.

Venipuncture risks:

There is a small risk of fainting or bruising and a 1/1000 risk of infection at the site where the blood is drawn.

Loss of confidentiality:

There is also a risk of loss of confidentiality.

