6.1.2 DOSING AND ADMINISTRATION

Site pharmacies will be unblinded and responsible for creating and supplying placebo for this study, as well as reconstituting Mepolizumab for dosing in this study. Mepolizumab will be provided to sites in 100 mg per vial as a sterile, single-use, lyophilized product in labeled 10 mL Type I clear glass, stoppered vials. The drug product must be stored in a refrigerator at a temperature of 2° C to 8° C (36° F to 46° F), protected from light. The recommended storage condition and expiry date where required, are stated on the product labels. Aseptic techniques must be used at all times when preparing this sterile product for administration.

Study drug should not be given to subjects if febrile (temperature of 100.4F/38C or greater). Study drug can be administered upon resolution of fever and approval by the site-investigator. Dosing may also be withheld if there are other patient concerns and at the discretion of site-investigators.

The drug product does not contain a preservative. Therefore, it is considered a single dose product. The reconstituted solution should be kept at refrigerated or controlled room temperature (up to 25° C). It should be used as soon as possible and any unused solution remaining after 8 hours should be discarded.

All subjects will receive 3 subcutaneous injections at each dosing visit. The 3 injections will be: 3 injections of 100mg mepolizumab each, or 3 injections of placebo, or 2 injections of placebo and one injection of 100mg mepolizumab depending on randomization and study visit (at the 3-month visit, subjects previously receiving placebo will receive 100mg of mepolizumab). The relation to meals is not important with this medication.

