7 STUDY INTERVENTION DISCONTINUATION AND PARTICIPANT DISCONTINUATION/WITHDRAWAL

7.1 DISCONTINUATION OF STUDY INTERVENTION

Subjects may choose to withdraw from participation in the study at any time upon their request without penalty. Additionally, the investigator and sponsor may withdraw a subject from the study in the event of an intercurrent illness, adverse event (AE), treatment failure, protocol violation, cure, and for administrative or other reasons. Discontinuation from study treatment does NOT automatically lead to a complete withdrawal from the study. Subjects discontinuing from study treatment are strongly encouraged to complete early termination procedures and safety follow up.

Investigators should withdraw study treatment from subjects if any of the following occur:

- Pregnancy
- Lost to follow up
- Hypersensitivity / systemic allergic reaction to the study treatment requiring administration of epinephrine
- The subject meets an exclusion criterion (either newly developed or not previously recognized) that precludes further study participation

- Worsening symptoms or disease progression that, in the opinion of the investigator, requires either esophageal dilation or EoE treatment with either topical or systemic steroids during the treatment period
- Any adverse event that, in the opinion of the investigator, precludes safe continuation with the study protocol and study dosing
- Significant study intervention non-compliance, in the opinion of the investigator
- Any condition that, in the judgment of the site-PI or Sponsor, would compromise the ability of the patient to comply with the study protocol or complete the study

Before deciding to discontinue study treatment, the site-PIs should consult the Sponsor-Investigator and study medical monitor, regardless of the reason for discontinuation. Subjects who withdraw and have received at least 1 dose of study drug should return to complete the early termination visit.

The reason for participant discontinuation or withdrawal from the study will be recorded on the eCRF. Subjects who sign the informed consent form and are randomized but do not receive the study intervention may be replaced. Subjects who sign the informed consent form, and are randomized and receive the study intervention, and subsequently withdraw, or are withdrawn or discontinued from the study, will also be replaced such that the goal enrollment at the end of the study can be achieved.

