8.8.2 DEFINITION OF SERIOUS ADVERSE EVENTS (SAE)

An adverse event (AE) or suspected adverse reaction is considered "serious" if, in the view of either the site-investigator or sponsor (UNC), it results in any of the following outcomes: death, a life-threatening adverse event, inpatient hospitalization or prolongation of existing hospitalization, a persistent or significant incapacity or substantial disruption of the ability to conduct normal life functions, or a congenital anomaly/birth defect. Important medical events that may not result in death, be life-threatening, or require hospitalization may be considered serious when, based upon appropriate medical judgment, they may jeopardize the participant and may require medical or surgical intervention

to prevent one of the outcomes listed in this definition. Examples of such medical events include allergic bronchospasm requiring intensive treatment in an emergency room or at home, blood dyscrasias or convulsions that do not result in inpatient hospitalization, or the development of drug dependency or drug abuse.

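### Sections 2.2.1 and 7.1 set different stopping rules after a hypersensitivity reaction, and the 7.1 withdrawal list is the narrower one

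*Combined protocol and SAP*

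**What the plan says.** Section 2.2.1 lists anaphylaxis, angioedema, bronchospasm, hypotension, urticaria and rash as examples of hypersensitivity reactions, and then says: "In the event of a hypersensitivity reaction, mepolizumab will be discontinued". No grade, seriousness or treatment threshold is attached. For helminth infection that does not respond to treatment, the same section is softer: "temporary discontinuation of mepolizumab should be considered".

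Section 7.1 gives the list of events after which investigators should withdraw study treatment. Its only allergy item is "Hypersensitivity / systemic allergic reaction to the study treatment requiring administration of epinephrine". Other reactions can reach the list through general items, chiefly "Any adverse event that, in the opinion of the investigator, precludes safe continuation with the study protocol and study dosing", and through a last item that turns on the judgment of the site investigator or the sponsor.

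Section 6.1.2 (dosing) has one specific hold: "Study drug should not be given to subjects if febrile". For the rest it says: "Dosing may also be withheld if there are other patient concerns and at the discretion of site-investigators".

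Section 8.8.2 gives, as an example of a serious event, "allergic bronchospasm requiring intensive treatment in an emergency room or at home". Section 8.8.9 makes anaphylaxis, and acute allergic reactions needing immediate treatment, events of special interest with 24-hour reporting.

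**The concern.** Site staff deciding whether to give the next injection would naturally turn to the withdrawal list, not to the risk narrative. The list is narrower than the narrative. Its epinephrine qualifier also invites the inference that an allergic reaction treated by other means may be followed by further dosing. That would include reactions the protocol itself treats as grave: bronchospasm that meets the serious-event definition, or an acute allergic reaction that meets the special-interest definition.

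What is at stake is participant safety and uniform conduct across the 4 sites. Two sites could handle the same reaction differently, each with a section of the protocol to cite.

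**Working it through.** The check is mainly a comparison of text. Both sentences are current protocol wording.

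**Step 1. What each section does to the affected patient's next dose**

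| Section | Trigger | Consequence for that patient's dosing |
|---|---|---|
| 2.2.1 | Hypersensitivity reaction, unqualified | Stop |
| 7.1, allergy item | Reaction that needed epinephrine | Should be withdrawn |
| 7.1, general items | Any adverse event or condition, by investigator or sponsor judgment | Discretionary |
| 6.1.2 | Fever | Hold until resolved |
| 6.1.2 | Other patient concerns | Discretionary |
| 8.8.7 | Serious adverse event | None stated; immediate report to sponsor |
| 8.8.9 | Acute allergic reaction needing immediate treatment | None stated; report within 24 hours |
| 9.4.6 | Serious adverse event | None stated; DSMB review as reported |
| 10.1.2 | Related or possibly related grade 3, 4 or 5 event | None stated; DSMB involvement, and suspension of screening and enrollment (for grade 3, on the second event) |

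**Step 2. The gap.** The reactions covered by 2.2.1 but not by the 7.1 allergy item are all hypersensitivity reactions managed without epinephrine. For these, 2.2.1 is the only text that requires a stop. Every other route is a review step or a matter of judgment.

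**Step 3. Direction of the consultation step.** Section 7.1 asks sites to consult the sponsor-investigator and medical monitor before stopping treatment. It asks for no such consultation before continuing after a reaction.

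**Step 4. Re-exposure for one patient, worst case.** The Schedule of Activities gives study drug at months 0, 1, 2, 3, 4 and 5.

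- 300 mg arm: 6 doses. After a reaction to dose k, 6 − k remain: 6 − 1 = 5 after the first dose and 6 − 5 = 1 after the fifth.
- Former placebo arm: 100 mg at months 3, 4 and 5, so 3 active doses. After a reaction to the first, 3 − 1 = 2 remain.

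**Step 5. Number of patients.** Section 2.2.1 gives rates of systemic allergic or hypersensitivity reactions of 4% (placebo 1%) and 0% (placebo 0%) in the two 300 mg programs, and 1% (placebo 2%) at 100 mg. None is broken down by severity or epinephrine use, so the number falling in the gap cannot be computed.

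**The case against.** The strongest reply is that there is no contradiction. If the 2.2.1 sentence is a rule, every hypersensitivity reaction is already a stop. The 7.1 list gives sufficient reasons to withdraw treatment, not the only ones, so a site that stops complies with both. If 2.2.1 is only narrative, 7.1 governs, and an epinephrine threshold plus clinical judgment is the sponsor's choice. Reading 2.2.1 as a rule because the helminth wording is softer is interpretation.

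The safeguards are also substantial. Patients are observed for 1 hour with vital signs at 5, 30 and 60 minutes, and are contacted again at 48 hours (6.2.4). The next dose is a month away, while serious or acutely treated reactions are reported at once or within 24 hours. The medical monitor can be unblinded for a safety concern (6.3). A patient who newly meets an exclusion criterion that precludes further participation should also be withdrawn (7.1), and criterion 13 in 5.2 covers conditions posing unreasonable risk.

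Much of this stands. A reader might infer that 7.1 permits or directs re-dosing after a serious allergic reaction, or that nobody outside the site would look at such a case. The documents support neither: 7.1 does not forbid stopping, and outside review exists. A reader might also multiply the quoted reaction rates by the arm size, or treat 5 doses as the expected exposure. The rates cover all such reactions, and 5 doses would require the investigator, sponsor and DSMB all to let dosing continue each month.

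What survives is narrower. The two sections state different thresholds, the one a site would act from is the weaker, and the review steps may lead to a stop but do not require one.

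**Conclusion.** The inconsistency is real and worth correcting. Section 2.2.1 stops drug after a hypersensitivity reaction without qualification. Section 7.1 names only reactions that needed epinephrine and leaves the rest to investigator or sponsor judgment. A site working from 7.1 alone could therefore re-dose a patient whom 2.2.1 says must stop.

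The scale is modest: few patients, a number that cannot be derived, and a per-patient worst case of 5 further 300 mg doses or 2 further 100 mg doses. The conclusion assumes that the 2.2.1 sentence is meant as a rule and that the epinephrine qualifier applies to both halves of the 7.1 bullet, which is its natural reading. If the sponsor regards 2.2.1 as narrative only, the two sections still need to agree. The sample size calculation and the method of primary analysis are not in question.

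**What to change.** Replace the epinephrine bullet in 7.1 with:

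> Anaphylaxis, or any systemic allergic/hypersensitivity reaction to study treatment that requires epinephrine, is serious (8.8.2), or meets the acute allergic reaction event of special interest (8.8.9); after any other suspected hypersensitivity reaction, study drug is held and, consistent with 2.2.1, discontinued unless the medical monitor determines that it was not a hypersensitivity reaction to study drug.

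Leave the 2.2.1 sentence unchanged and add a cross-reference to 7.1. Narrowing 2.2.1 to match 7.1 would also remove the conflict, but it would loosen the stricter rule for reactions such as urticaria and rash, so it is not the better edit.

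The cost is one bullet and one cross-reference, with no change to visits or planned analyses. There may be a few more treatment discontinuations, partly because 8.8.9 does not define immediate treatment. Sites are blinded, so suspected reactions to placebo would be held too. Stops after the doses at months 0, 1 or 2 come before the month 3 assessment. Some of those subjects may therefore lack the 3-month EEsAI and endoscopy data that the modified ITT set in 9.3 requires, although 7.1 encourages early termination procedures and replaces subjects who withdraw.

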2.2.2 KNOWN POTENTIAL BENEFITS

The potential benefit of mepolizumab is related to its effect as a treatment for EoE. This medication is able to block eosinophil development and activation, thereby substantially decreasing eosinophil levels both in the blood and in the tissue. This decrease in eosinophils, should, in turn, decrease clinical symptoms related to EoE. Specifically, the cytokine IL-5 has been shown to play a major role in EoE pathogenesis.^{30, 31} IL-5 is increased in patients with EoE, leads to production of IL-13, which in turn stimulates the esophageal epithelium to produce eotaxin-3, a potent chemokine that recruits eosinophils to the esophagus.³² In experimental models of EoE, blocking IL-5 attenuates the disease state, whereas overexpression of IL-5 creates an EoE-like phenotype.^{31, 33} Mepolizumab is a recombinant monoclonal antibody that binds IL-5 and has been demonstrated to be highly effective in eosinophilic diseases such as HES,³⁴ eosinophilic asthma,^{35, 36} and most recently eosinophilic granulomatosis with polyangiitis.³⁷ Because of its mechanism of action, mepolizumab is a highly promising therapeutic agent for EoE, and has previously been studied in this condition. A small randomized clinical trial (RCT) in 11 adults showed a good histologic effect (55% decrease in mean tissue eosinophil levels in the mepolizumab arm vs 7% decrease in the placebo arm), but variable symptom response.³⁸ A larger RCT examining three dosing regimens in 59 children also showed a good histologic effect (peak eosinophil count decreased from 118 eosinophils per high-power field [eos/hpf] to 24 eos/hpf in the 2.5 mg/kg arm), but symptoms were relatively mild at baseline and there was no clear overall trend towards

improvement.³⁹ In this study, it is likely that mepolizumab will decrease blood and tissue eosinophil counts, and we hypothesize that this will also decrease clinical symptoms of dysphagia.

2.2.3 ASSESSMENT OF POTENTIAL RISKS AND BENEFITS

Because the prior studies of this medication in adults and adolescents (who are the target population for this study) have been very small and did not require a symptom threshold for entry, we feel that the current study as designed is required to assess efficacy of this drug. The potential value of information gained, specifically related to a novel therapy for EoE that can be applied for highly symptomatic, and potentially refractory patients, is the basis for exposure to the potential risks of the study. Risks will be minimized by the study design which will have an active and extensive surveillance protocol for adverse events (AEs), as well as close monitoring during and after study drug administration. Finally, the inclusion of a placebo arm is justifiable as there are currently no FDA-approved medications for EoE, and the 3-month long placebo period is very short given the chronic nature of EoE (for example, many patients have a symptom duration of 5-10 years prior to diagnosis).

